8.3 Statistical methods

The primary aim is to test whether liraglutide reduces craving in patients recovering from OUD in residential treatment. Analysis of covariance (ANCOVA) will be used to compare liraglutide versus placebo treatment groups controlling for baseline values of craving. Linear mixed effects models for repeated measurements will also be used to evaluate the difference in changes in these primary outcomes between treatment groups. The baseline and post-treatment outcomes are treated as dependent variables in the mixed model. Subjects with missing values can be incorporated in the mixed model analysis when data are missing at random. The moderating effect will be assessed by adding the interaction term between moderator and treatment group in the models.

SAS (version 9.4) and R (version 3.2.5) software will be used for analyses with a significance level of 0.05. Summary statistics including means, medians, ranges, and standard deviations will be computed for each continuous variable and frequencies with percentages for categorical variables. Identified data outliers will be further examined to determine if they are data entry errors, in which case they will be modified when possible; otherwise, values will be kept for final analysis.

Primary outcomes to assess efficacy are: (1) cue-elicited drug craving rated on a 100-pt VAS; and (2) ambient drug craving, derived from EMA of daily craving throughout the study period. Data analyses for cue-elicited craving will consist of a 2×2 ANOVA with medication status (pre- vs post-medication) as a within-group variable and medication type (liraglutide vs placebo) as a between-group variable.

Secondary analyses of self-reported craving measures will evaluate the role of MAT, specifically BUP/NA, in these results.

EMA and Wearable Assessment: Ambient drug craving derived from the EMA will be analyzed as a multilevel model in the regression framework and will test effects of medication status within-person and medication type between-person. Secondary analyses of EMA will examine the effect of time (e.g. study day) to identify differences across condition in the rate of decline in craving across time.

Data reduction including derivation of summary features for continuously collected data (e.g., sleep data, physiological data) will be performed before formal statistical analysis. Descriptive analysis will be performed to explore distributions of data and identify potential outliers. Assumptions and goodness of fit of statistical models will be assessed. Missing data, including mobile and ambulatory attrition and drop-out will be examined to ensure the validity of statistical models used. Because ambulatory and mobile monitoring will continue during laboratory assessment days, correlation analyses will be used to confirm the agreement between corresponding measures from the two approaches; this will both speed harmonization for follow-up analyses, and provide additional validation of the measures used in the both cases.

The primary endpoints of the EMA assessment will be the rate of reduction of craving across the approximately 21 day study period in the treatment condition compared to the control condition while controlling for the traditional craving triggers of sleep, stress, hunger, affect, and pain and discomfort. Sleep and activity will be measured using a multimodal approach with self-report via the morning EMA survey and wearable actigraphy to measure and account for subjective biases in sleep timing. Craving reduction will be primarily measured using EMA assessment, and will be modeled using linear mixed models in the multilevel modeling (MLM) framework. In MLM, subject-specific random effects are combined with population-level fixed effects to account for variability both within each individual and between individuals in a manner that allows participants with incomplete data to be included in the model. Craving reduction will be modeled as an effect of time in treatment, and differences in rate of craving reduction will be tested as an interaction between treatment state and time. Drs. [name], [name], and [name] each have extensive experience analyzing similar data in the multilevel modeling framework.

For secondary safety outcomes, intensive longitudinal methods such as time-varying effect models will be used to assess for changes in continuously measured outcomes (e.g. blood pressure, heart rate, respiratory rate, body weight) to account for repeated measures. The proportion of participants experiencing AE and SAE will be compared between treatments using chi-square analysis.

For exploratory outcomes, analysis of fNIRs-based neuroimaging will utilize a 2 (Medication Status) x 2 (Medication Type) ANOVA to evaluate the change in oxygenation in prefrontal cortex in response to opioid drug cues vs neutral cues, with a region of interest in left middle frontal gyrus. Analysis of safety outcomes from baseline to the end of target dose and to end of rebound follow-up will be analyzed using intensive longitudinal methods similar to the analysis of secondary outcomes. Changes in indices of glycemic control measured at baseline and at end of the target dose (e.g. HgA1c, fructosamine) will be calculated as deltas, with comparisons made between treatments using unpaired t-tests or Mann Whitney U tests as appropriate.

Interim Power Analysis: one or more interim power analyses may be conducted during the study to assess the effect size needed to observe a significant drug effect for primary, secondary, and/or exploratory endpoints based on the data collected at that time. These analyses would not bias type 1 error rates and the study team will use this information to determine whether and when to perform an interim data analysis to justify advancement to the second phase of the funding award (UH phase). In particular, the confidence intervals around the parameters representing the primary endpoint will be used as an approximation of the power available for our primary endpoints using the current data. This

will be weighed against the original proposed power and the PI's estimates of likely power after completion of the grant period to determine whether an interim analysis is warranted.

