7.4.3 Method for Assigning Subject to Treatment Groups

Participants will receive either liraglutide or placebo in a two-arm parallel group study. Interventions will be randomized in a 1:1 ratio using permuted-block randomization algorithm. The randomization will be performed using a random number generator via the PLAN procedure within SAS software, version 9.4 (SAS Institute Inc., Cary, NC). Personnel in the Department of Public Health Sciences (PHS) will use the PLAN procedure within SAS software to generate a randomization list using variable-size, random permuted blocks to ensure that the number of participants in each arm is balanced after each set of B randomized participants, where B is the block size. Personnel in PHS will choose the block sizes without revealing it to any of the investigators or study personnel who will be collecting and reviewing outcomes data. The randomization sequence will be uploaded to a secure REDCap database. Synergy Pharmacy will be given access to this REDCap database to provide the blinded, randomized labeling prior to shipping the study drugs to the CaronTC

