8.2 Sample size determination

This is an exploratory study to accumulate pilot data. The primary endpoint of this study is cue-elicited self-reported craving VAS scores. A sample size of N=20 per group will give 80% power to detect an effect size of 0.91 based on a two-sided two-sample t-test with a significance level of alpha=0.05. Accounting for an estimated 20% attrition rate, we plan to randomize a total of 20*2/0.8=50 patients in the study. To preserve statistical power, the sample will not be balanced with regard to MAT and non-MAT participants.

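### The moderator-by-arm term fits the ANCOVA, but in models that carry baseline as an outcome it does not estimate moderation of the treatment effect; a moderator-by-arm-by-time term is needed there

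*Combined protocol and SAP*

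**What the plan says.** Section 8.3 (Statistical methods) first names an ANCOVA of craving adjusted for its baseline value. It then adds a second model: "Linear mixed effects models for repeated measurements will also be used to evaluate the difference in changes in these primary outcomes between treatment groups". For that model, "The baseline and post-treatment outcomes are treated as dependent variables in the mixed model". Moderation follows in the same paragraph, with one rule for what precedes it: "The moderating effect will be assessed by adding the interaction term between moderator and treatment group in the models".

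Later in Section 8.3, cue-elicited craving is also to be analysed by a 2×2 ANOVA with pre/post medication as the within-subject factor and arm as the between-subject factor. For ambient craving, the primary EMA endpoint is the rate of reduction, and "differences in rate of craving reduction will be tested as an interaction between treatment state and time".

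The moderator is not named. A separate paragraph of Section 8.3 says that secondary analyses of self-reported craving will look at the role of MAT (BUP/NA). Section 8.2 says the sample will not be balanced on MAT. The plan nowhere states a moderator-by-treatment-by-time term.

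**The concern.** What a two-way moderator-by-arm term means depends on what the model treats as the outcome. In the ANCOVA the outcome is the post-treatment score, the arm coefficient is the treatment effect, and moderator by arm is its moderation.

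When baseline is itself an outcome, the treatment effect is arm by time. Its moderation is then moderator by arm by time. A moderator-by-arm term without time is a single contrast held constant over all visits. It includes Day 1, before the first dose on Day 2, when no drug effect can exist. It also absorbs any chance baseline difference between the moderator-by-arm cells. The same holds if the rule is applied to the pre/post ANOVA.

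In the EMA model, where the stated effect is a slope difference, the two-way term concerns the level of craving and not its rate of decline.

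At stake is whether a planned secondary analysis, most plausibly the one on MAT, answers the question it asks. The mixed model is also the one chosen to keep participants with missing values, so its moderation result could carry weight in the report.

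**Working it through.** **1. The plan's own figure.** Section 8.2: "A sample size of N=20 per group will give 80% power to detect an effect size of 0.91", from a "two-sided two-sample t-test with a significance level of alpha=0.05". The exact noncentral t calculation gives 80.1% power (detectable effect 0.909). Then 40/0.8 = 50, as stated. The sample size reproduces and is not in question.

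**2. What the two-way term estimates with two cue visits (Days 1 and 19).** Let D0 and D1 be the moderator-by-arm contrasts of cell means at baseline and post-treatment. For a moderator fixed before randomisation, E(D0) = 0 and E(D1) = δ, the true moderation. The model holds time, arm, arm×time, moderator, moderator×time and moderator×arm. Its generalised least squares estimate of moderator×arm is (1 − w)·D0 + w·D1, with

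w = (1 − ρs) / (1 + s² − 2ρs),

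where s is the post/baseline SD ratio and ρ the pre-post correlation. Neither is in the documents; the ranges below are assumptions. The expected coefficient is wδ.

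| Post/baseline SD ratio s | ρ = 0.3 | ρ = 0.5 | ρ = 0.7 |
|---|---|---|---|
| 0.7 | 0.74 | 0.82 | 1.00 |
| 1.0 | 0.50 | 0.50 | 0.50 |
| 1.3 | 0.32 | 0.25 | 0.10 |

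Example: s = 1.3, ρ = 0.7 gives (1 − 0.91)/(1 + 1.69 − 1.82) = 0.09/0.87 = 0.10.

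Other cases:
- Equal SDs with 20% of post values missing: 0.41 to 0.43.
- Three visits (Days 1, 19, 31), equal SDs, the same effect at both later visits, ρ = 0.5: 0.67.
- Arms constrained equal at baseline, equal SDs: 0.27 to 0.30.

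Adding moderator×arm×time gives D1 − D0 in the two-visit case. It recovers 1.00·δ in every two-visit case in the table, and in the EMA slope case in step 4.

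**3. Power.** Assumptions: 40 completers, 10 per moderator-by-arm cell (an equal split that the plan does not promise), SD 1 at both visits, and a moderation of 0.91 SD, borrowed from Section 8.2 for scale. Noncentral t, 36 df (35 for ANCOVA).

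- Two-way term, mixed model: expected δ/2 = 0.455, SE = √(4·((1 + ρ)/2)/10)
- Three-way term: expected δ = 0.91, SE = √(4·2(1 − ρ)/10)
- ANCOVA two-way term: expected δ = 0.91, SE = √(4·(1 − ρ²)/10)

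| ρ | Two-way, mixed: SE, power | Three-way: SE, power | ANCOVA two-way: SE, power |
|---|---|---|---|
| 0.3 | 0.510, 14% | 0.748, 22% | 0.603, 31% |
| 0.5 | 0.548, 13% | 0.632, 29% | 0.548, 37% |
| 0.7 | 0.583, 12% | 0.490, 44% | 0.452, 50% |

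An unequal MAT split would raise every SE.

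**4. EMA model.** The 3-dose schedule in Section 7.2 lists Days 1–3, 6–9, 12–15 and 18–21: 3 + 4 + 4 + 4 = 15 days, of which only Day 1 is pre-drug.

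- If moderation is a step once dosing starts, the two-way term keeps 14/15 = 0.93 under a random intercept, or 0.83 with an assumed random slope. Pre-drug averaging is minor.
- If moderation acts on the slope, the two-way term returns the average of (day − 1)/20 over the 15 days. That is (168 − 15)/20/15 = 0.51 of the Day 21 effect under a random intercept, or 0.20 with the assumed random slope. This loss comes from leaving out the interaction with time.

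Assumed variance components: intercept 1, residual 0.5, and slope 0.5 on the 20-day scale where used.

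**The case against.** The strongest reply is that Section 8.3 describes its models in prose and writes none of them out. It does not spell out arm by time for the first mixed model either, so the moderation sentence may be shorthand for interacting the moderator with whatever the treatment effect is. That is possible. But the sentence names a specific term, comes right after the mixed model is described, and is the only rule given. An analyst who followed it literally would fit the wrong contrast.

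Second, a valid test already exists. The ANCOVA is named first, the two-way term is correct there, and in the table above it has more power than the three-way term at each correlation. This stands for cue craving. The EMA rate-of-decline endpoint has no stated ANCOVA counterpart.

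Third, two links are inferences. The moderation sentence precedes the EMA text, and the plan does not say that it reaches the EMA model. Section 8.3 is also not uniform on EMA: it first describes effects of medication status and type, with study day as secondary, and later makes the rate of reduction primary. Nor does the plan say that MAT is the moderator. Both points stand, so the EMA part is conditional and the moderator should be named.

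Fourth, this is a secondary analysis in a self-described exploratory pilot, and moderation power is low whichever term is used. That limits the consequence. It does not make the contrast right.

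**Conclusion.** Wrong as written, limited to a secondary analysis. In the mixed model, and in the pre/post ANOVA if the rule is used there, moderator by arm does not estimate moderation of the treatment effect. What it does estimate depends on the SD ratio, correlation, missingness and number of visits.

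A reader might infer that the term always halves the effect. That holds exactly only for two visits, equal SDs and complete data. Otherwise the share runs from about 0.1 to 1.0 over the SD ratios and correlations assumed here, and is 0.67 with three visits.

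A reader might also infer that pre-drug dilution is the problem in the EMA model. With 1 of 15 days pre-drug it is not; the fault there, if the rule applies, is the missing interaction with time.

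Nor do the documents support saying that the plan lacks any valid moderation test, or that the primary comparison or the sample size is affected. The power figures rest on assumed correlations, an assumed 0.91 SD moderation and an assumed equal moderator split.

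**What to change.** Replace the moderation sentence in Section 8.3 with text to this effect: in the ANCOVA, moderation is tested by moderator × treatment, with the moderator main effect in the model; in the linear mixed model, the pre/post ANOVA and the EMA multilevel model, it is tested by moderator × treatment × time (pre/post or study day), with all lower-order terms. Name MAT (BUP/NA) as the moderator if that is the intention, and list any others. Report the moderation estimate with its 95% CI, since a p-value alone will say little at this sample size.

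The cost is one or two sentences. No visits, data or participants are added, and the sample size does not change.

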1.2 Primary Study Endpoints

The primary objectives of this pilot study are 1) to determine whether liraglutide can reduce cue-elicited drug craving over 3-5 weeks while participants are in residential treatment for OUD, and 2) to study whether liraglutide can reduce ambient (daily) drug craving over approximately 21-33 days while participants are in residential treatment for OUD.

- 1) Cue-elicited Drug Craving. Change in self-reported cue-elicited drug craving from baseline (Day 1) to the end of the target drug dose (Day 19 [and additionally until Day 31 for 5-dose intervention]) will be measured on a 0-100 point visual analog scale (VAS), where 0= no craving, 100= maximum craving. Assessments are taken prior to, and immediately after, exposure to visual drug cues in the Cue Response Task.
- 2) Ambient Drug Craving. Change in ambient drug craving over time will be measured throughout the study (Days 1-21 [and additionally until Day 33 for 5-dose intervention]) using a 0-100 VAS delivered via smartphone using Ecological Momentary Assessment (EMA) 4 times per day, on each test day (Days 1 and 19 [and additionally Day 31 for the 5-dose intervention]) and on the first two days and last 2 days of each treatment dose.

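### Section 8.3 gives cue-elicited craving three analyses and names none primary; the 2×2 ANOVA it states last is usually, though not always, less precise than the ANCOVA it already lists

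*Combined protocol and SAP*

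**What the plan says.** Section 8.3 describes three analyses that apply to cue-elicited craving.

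- For the primary aim: "Analysis of covariance (ANCOVA) will be used to compare liraglutide versus placebo treatment groups controlling for baseline values of craving".
- A linear mixed model is also to be used for the primary outcomes: "The baseline and post-treatment outcomes are treated as dependent variables in the mixed model". Its stated advantage concerns missing data: "Subjects with missing values can be incorporated in the mixed model analysis when data are missing at random".
- Two paragraphs later, the analyses for cue-elicited craving "will consist of a 2×2 ANOVA with medication status (pre- vs post-medication) as a within-group variable", with arm as the between-group factor.

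No sentence ranks the three, and the significance level is 0.05 throughout. Section 8.2 sizes the trial with a fourth method, a two-sample t-test.

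The VAS is recorded twice per test day. Section 1.2 says: "Assessments are taken prior to, and immediately after, exposure to visual drug cues in the Cue Response Task". Section 8.3 does not say whether the pre-cue score, the post-cue score or their difference is analysed.

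On which outcome is primary, section 8.2 says: "The primary endpoint of this study is cue-elicited self-reported craving VAS scores". Section 8.3 says: "Primary outcomes to assess efficacy are: (1) cue-elicited drug craving rated on a 100-pt VAS; and (2) ambient drug craving". Sections 1.2 and 9.2 also name two.

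For HbA1c and fructosamine, section 1.4 (item 6) ends the change at Day 19, with Day 31 in brackets for the 5-dose intervention. Sections 1.3 (item 3), 7.2 and 9.4 describe Day 31 as an extra measurement on top of Day 19. Section 8.3 compares arms on deltas from baseline to the end of the target dose.

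**The concern.** A reader of section 8.3 cannot tell which test will produce the cue-craving result. The tests are not interchangeable: two of them can give different answers on the same data, and they generally differ in precision.

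The trial is a pilot, but its results have a use. Section 2.3 makes a trend towards efficacy, together with safety, the basis for a multi-centre trial. The interim paragraph of 8.3 uses confidence intervals for the primary-endpoint parameters to decide whether an interim analysis is warranted. The width of those intervals depends on the model. With about 40 evaluable participants, precision that costs nothing is worth having.

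**Working it through.** **1. The plan's own figure.** Inputs from section 8.2: 20 per arm, effect size 0.91, two-sided t-test, alpha 0.05, 20% attrition. The noncentral t distribution with 38 df gives power 80.1%, and 20 × 2 / 0.8 = 50. Both stated figures reproduce.

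**2. Variances.** Let r be the Day 1 to Day 19 correlation (assumed; the documents give none), and take equal pre and post SDs. In units of the squared SD:
- ANOVA arm-by-time term (a t-test on the change score): 2(1 − r)
- ANCOVA on baseline: 1 − r²
- Large-sample ratio: 2(1 − r)/(1 − r²) = 2/(1 + r)

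With 40 analysed, estimating the ANCOVA slope multiplies its variance by about 1 + 1/(40 − 4) = 1.028.

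| r | 2(1 − r) | 1 − r² | Large-sample ratio | Simulated ratio, 20 per arm |
|---|---|---|---|---|
| 0.3 | 1.40 | 0.91 | 1.54 | 1.50 |
| 0.5 | 1.00 | 0.75 | 1.33 | 1.30 |
| 0.7 | 0.60 | 0.51 | 1.18 | 1.14 |

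Multiplying 20 by the simulated ratio, the ANOVA would need about 30, 26 or 23 per arm to match ANCOVA with 20.

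**3. Power.** Section 8.2 does not say which SD scales the 0.91, so both readings are shown. Simulation: bivariate normal, 200,000 trials per cell.

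| r | ANOVA, raw SDs | ANCOVA, raw SDs | Tests disagree, raw SDs | ANOVA, change SDs | ANCOVA, change SDs |
|---|---|---|---|---|---|
| 0.3 | 66% | 83% | 21% | 80% | 93% |
| 0.5 | 80% | 89% | 12% | 80% | 89% |
| 0.7 | 95% | 97% | 3% | 80% | 85% |

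The gain is small above r of about 0.7. At r = 0.8 the raw-SD powers are 99.3% and 99.6%.

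**4. Unequal SDs.** If the post SD is k times the pre SD, the large-sample ratio is (1 + k² − 2rk) / [k²(1 − r²)].
- k = 0.75: 2.17, 1.93, 1.79 at r = 0.3, 0.5, 0.7. The gain is larger.
- k = 1.25: 1.27, 1.12, 1.02 at the same r. At r = 0.8 it is (1 + 1.5625 − 2)/(1.5625 × 0.36) = 1.00. With the slope estimated at 20 per arm, these become 1.24, 1.09, 0.99 and, at r = 0.8, 0.97. In the last two cells the ANOVA is marginally the more precise test.

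**5. The mixed model.** With complete data at two visits, its arm-by-time estimate equals the change-score difference if the baseline means are free to differ by arm. It equals the ANCOVA estimate if they are held common. Fits by maximum likelihood agreed to within 0.00001 in each case. Section 8.3 does not say which is meant.

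**6. Glycemic delta.** Day 2 to Day 19 is 17 days; Day 2 to Day 31 is 29 days. Under section 7.1, extension depends on length of stay and on the participant's choice, and may be settled as late as Day 18. If section 1.4 is read as replacing Day 19 by Day 31 for extenders, the pooled delta mixes the two lengths.

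**The case against.** **Precision depends on unknowns.** The documents give neither r nor the two SDs, and step 4 shows cells where the ANOVA is level or slightly ahead. This stands: a reader might infer that the ANOVA is always the weaker test, and the documents do not support that.

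**The mixed model may be sound.** Treating baseline as an outcome fits a common-baseline model as well as a free one. This stands. One cannot say from the text that the mixed model is a second change-score test, only that its form is unstated.

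**The time point is largely settled.** Section 1.2 defines change from Day 1 to Day 19, with Day 31 additional, and section 7.2.5 has Day 19 measured whatever the intervention length. This stands in substance, although 8.3 should repeat it. It does not settle which VAS score is used.

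**EMA is not put above cue craving.** One might infer a further conflict from "Craving reduction will be primarily measured using EMA assessment". That sentence sits in the EMA and wearables part of 8.3 and can be read as EMA rather than wearable data. The remaining disagreement is 8.2 (one primary endpoint) against 1.2, 8.3 and 9.2 (two).

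**It is a pilot.** Progression rests on a trend and on safety, not on p < 0.05. One could compute a type I error of 7.8%, 7.3% or 6.7% (r = 0.3, 0.5, 0.7) if either test could be claimed, but nothing in the documents says that either may be. The pilot status lowers the stakes without telling the reader which analysis gives the result.

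**The glycemic wording may be loose drafting.** Three sections treat Day 31 as additional, so a biased comparison is not established.

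**Conclusion.** The point holds in a qualified form. Three analyses of cue-elicited craving are listed without a ranking, and the wording last settles on a change-score ANOVA. This part is read directly from 8.3 and is firm.

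The size of the loss is less certain. The variance excess of about 50%, 30% and 14% rests on equal SDs, normal data, 20 evaluable per arm and an assumed r of 0.3, 0.5 and 0.7; the quoted power gap also assumes that 0.91 is in raw SDs. The loss is greater if the post SD is below the pre SD, and nil or slightly negative if it is about 1.25 times the pre SD with r at 0.7 or above.

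The sample size is not in error. The count of primary endpoints and the glycemic end day are textual conflicts to reconcile, with no size of bias established for either. The change should be made, but the ambiguity does not invalidate the trial.

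**What to change.** In section 8.3:

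- Name one primary analysis of cue-elicited craving: ANCOVA of the Day 19 value on arm and the Day 1 value, in all randomised participants with a Day 19 value, whether or not they extend.
- State which VAS score is used (pre-cue, post-cue or their difference) and use the same one at both visits. The choice is the sponsor's.
- Replace the 2×2 ANOVA as the stated analysis of this outcome, or label it a sensitivity analysis.
- Keep the mixed model as supportive and state a common baseline mean across arms.
- Report Day 31 cue-elicited craving separately, among those who extend.

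Elsewhere:

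- Reconcile 8.2 with 1.2, 8.3 and 9.2 on whether there are one or two primary endpoints.
- Reconcile 1.4 (item 6) with 1.3, 7.2 and 9.4 so that the between-arm HbA1c and fructosamine delta runs from Day 2 to Day 19 for everyone.

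**Cost.** Wording only, with no added participants, visits or measurements. The downside is that participants without a Day 19 value do not contribute to the ANCOVA. The two-visit mixed model with a common baseline mean gives the same arm difference, so it does not recover their outcomes.
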